3.3	
Sample size Describe calculation of sample size or reference to sample size calculation in study protocol
	
Primary outcome: Based on the randomised clinical study of myopic children using DIMS spectacle lenses (Lam et al. 2020) standard error of mean was 0.02 mm and $n = 79$ in the DIMS group, hence the standard deviation (Smith et al. 2010) was calculated to be $SE = \frac{SD}{\sqrt{n}}$ given a SD of 0.178 mm. Based on the CONTROL-study (Jakobsen & Møller 2021) the SD of the treatment effect after 18 months was 0.18 mm in the OKL group. A sample size calculation for a non-inferiority study between the two groups given a significance level of 0.025 (one-sided test) and a power of 80% with a mean difference between treatment groups of 0.13 mm and a SD of 0.18 mm the sample size for each group should be 32 children. With an expected drop out of 30% a total of 42 children will be needed in each group.
 
A difference of 0.13 mm was chosen with reference to the correlation between change in cycloplegic spherical equivalent refractive error and axial length equivalent to 0.25D for female subjects aged 6 to 12 years in a Danish population (Jakobsen, Gehr & Møller 2020). 0.25D is the minimum measurement increment of refraction itself. Thus, to conclude non-inferiority, the difference between the two treatments (DIMS and OKL) need to be equal to, or less than, 0.25 D after 18 months of treatment.
 
The dropout rate evaluation one month after the inclusion of the last participant showed a dropout rate of 20%. Consequently, after clinical and statistical considerations, we increased the

		
total number of participants from 84 to 90, which corresponds to a 40% dropout rate. This was to ensure the sufficient power of the study.
 
Sample size: 90 children Non inferiority margin: Minimal clinically important difference: 0.13 mm (= 0.25D), SD 0.18

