5.1	Eligibility Summarize in- and exclusion criteria	
Inclusion criteria:
 
 - Myopic children aged 6 to 12 years: Myopia of the 6 to 8-year-olds (inclusive): -1.00 to -4.75 D spherical component and up to -2.50 D of regular astigmatism (both eyes). Myopia of the 9 to 12-year-olds (inclusive): -2.00 to -4.75 D spherical component and up to -2.50 D of regular astigmatism (both eyes). - Anisometropia \leq 1.50 D cycloplegic spherical equivalent refractive error. - Best corrected visual acuity at age 6 to 12 years (inclusive): 0.8 Snellen (equivalent to \geq 3/5 letter on the 0.8 line = 78 ETDRS letters) 
Exclusion criteria:

	
 - Manifest or intermittent squint. - Contraindications to the use of OKL comprising (not exhaustive): keratoconus, chronic allergic conjunctivitis and keratoconjunctivitis sicca. - Previous eye surgery. - Chronic eye disease demanding daily use of eye drops. - Non-compliance to eye examinations (unstable fixation or anxiety towards contact lenses). - Previous myopia control treatment. 
After trial commencement, project staff confused criteria of best corrected visual acuity in the 9 to-12 years group with the criteria of the 6 to 8-years group resulting in four children of 9 years old included using the 6 to 8-years old criteria for best corrected visual acuity. No children were excluded by this mistake. Preliminary referral or screening was not based on the visual acuity criteria. The visual acuity criterium was chosen to screen for abnormal vision. After clinical considerations, the visual acuity inclusion criteria in the 9–12-year group was too strict, as some of the younger children may not have fully matured visual development as 9-year-olds. Hence the inclusion criteria was adjusted to age 6 to 12 years (inclusive): 0.8 Snellen (equivalent to $\geq 3/5$ letter on the 0.8 line = 78 ETDRS letters), which reflects the visual acuity criteria used in the CONTROL-study (Jakobsen & Møller 2021)

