6.2	
Primary analysis methods
 
Describe in details which statistical methods will be used (i.e. regression), how treatment effects will be presented (i.e. which effect measure - OR, HR etc.) and if estimates will be adjusted for covariates (see appendix). If analyses will be adjusted for covariates, describe how the sufficient adjustment set will be defined (i.e. using DAGs)
 
Describe methods used to check assumptions (i.e. normality, proportional hazards) behind the statistical models, and alternative methods if assumptions about distribution do not hold.
	
Primary outcome
 
Blinded interpretation of primary analysis: Study groups labelled as A & B is presented to the authors.
 
We will compare the two treatment groups with one linear mixed effects regression model with the participant as random intercept using axial length as the dependent variable and visit as the (categorical) independent variable, with baseline as reference point. Both eyes are used in the analysis.
 
Both an Intention to treat and a per-protocol approach will be performed.
 
The regression models will be reported as unadjusted, and as adjusted for the following covariates for a more precise result:
 
 - Age at baseline - Cycloplegic spherical equivalent refractive error at baseline - Axial length at baseline - Number of myopic parents (spherical equivalent refractive error $\leq -0.50D$) at baseline 
The adjusted model will also be adjusted for time-varying post-randomisation variable to explain the performance bias in the “effect” of adherence:
 
 - Non-wear (patient-reported as the participants total amount of days without OKL or hours without DIMS) 
The non-inferiority margin is 0.13 mm. Non-inferiority will be concluded if the upper bound of the 95% confidence interval for the estimated treatment difference (DIMS – OKL) after 18 months is equal to or below 0.13 mm, in both ITT and PP analyses.
 
Results will be presented as estimated coefficients with standard errors (SE), p-values (p) and 95% confidence intervals (CI):
 
 1) Mean axial elongation at each 6-month interval over 18 months by treatment group 2) Between-group differences in axial elongation at each time point. 
Model assumptions will be assessed using Q-Q plots for normality of residuals and random effects, and residual vs. fitted plots to check for homoscedasticity. If assumptions are violated (e.g. non-normality or heteroscedasticity), robust standard errors or non-parametric bootstrapping will be applied.
 
Key secondary outcome: A similar approach will be made for the key secondary outcome.

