6.3	Additional analysis methods	In case of non-inferiority, superiority is tested in the same population at 0.05 without a statistical penalty because of the

	
Describe any planned sensitivity and subgroup analysis including how subgroups will be defined (see appendix).
	
closed testing principle. Superiority is declared if the upper 95%CI bound is below zero (Figure 3).
 
In case of inferiority, a subgroup analysis of participants in the DIMS group with axial elongation exceeding emmetropic progression rate will be conducted as a hypothesis generating post hoc analysis.
 
Adherence: Sensitivity analysis of binary adherence “No-wear”, is repeated in groups of “high adherence”, “moderate adherence” and “low adherence” (see 4.2).
 
Protocol deviations: -Sensitivity analysis with and without the four children mistakenly included by technical error in the autorefractor apparatus result reading at baseline (see 4.2). Analysis is either provided in supplementary or by request.
 
-Sensitivity analysis of dropouts.
 
Additionally, post hoc analysis: - axial elongation after 18 months in relation to age at enrolment. - axial elongation after 18 months in relation cycloplegic spherical equivalent refractive error at baseline.

6.4	
Missing data Describe how missing data will be explored and which assumptions and methods will be used to handle missing data (i.e. multiple imputation)
	Missing data assumed to be missing at random (MAR) and will be handled by the mixed effects regression model.

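### A participant random intercept alone cannot represent two eyes at four visits, so the width of the confidence interval that decides non-inferiority is not controlled

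*SAP*

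**What the plan says.** Section 6.2 specifies "one linear mixed effects regression model with the participant as random intercept using axial length as the dependent variable", with visit as a categorical factor, and adds: "Both eyes are used in the analysis". The Table 3 and Table 5 footnotes repeat the participant random intercept and name no other random or residual structure. Section 3.6 places the measurements at baseline and every 6 months to 18 months, so each child contributes 2 × 4 = 8 readings. Non-inferiority is concluded if the upper 95% limit for DIMS minus OKL at 18 months does not exceed 0.13 mm, in both ITT and PP.

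The checks are: "Model assumptions will be assessed using Q-Q plots for normality of residuals and random effects, and residual vs. fitted plots". The remedy is conditional: "If assumptions are violated (e.g. non-normality or heteroscedasticity), robust standard errors or non-parametric bootstrapping will be applied". Section 6.4 adds: "Missing data assumed to be missing at random (MAR) and will be handled by the mixed effects regression model". The adjusted version is introduced with: "The regression models will be reported as unadjusted, and as adjusted for the following covariates for a more precise result".

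**The concern.** A participant intercept treats a child's eight readings as exchangeable apart from the fixed effects. Two features of axial length contradict this.

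- **Children grow at different rates, and both eyes share much of that growth.** This is the sampling variation that the sample size in section 3.3 rests on. The model has no term for it, so its interval tends to be too narrow.
- **The two eyes of a child differ in length at every visit.** This difference cancels from change since baseline. The model nevertheless counts it as residual noise, so its interval tends to be too wide.

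The upper limit of this interval is the whole decision rule. Too narrow means that a DIMS lens truly worse by the margin passes more often than 2.5% of the time. Too wide means that a truly non-inferior lens can fail. The superiority test in 6.3 uses the same interval, and the key secondary outcome uses a similar model.

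**Working it through.** **The plan's own figure.** With margin 0.13 mm, SD 0.18 mm and one-sided 0.025, the t-based calculation gives power 0.799 at 31 and 0.812 at 32 per group, so the stated 32 reproduces. It implies a standard error of 0.18 × √(2/32) = 0.045 mm, with between-child variation in growth as the error term.

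**Inputs from the SAP.** SD of 18-month change 0.18 mm (variance 0.0324); margin 0.13 mm; 90 children, so 45 per arm, or 36 per arm after the 20% dropout in 3.3. Section 6.1 gives smallest detectable changes of 0.025 and 0.041 mm. Dividing by 1.96√2 gives a reading-error SD of 0.009 to 0.015 mm, so nearly all variation in change is real growth.

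**Assumed, because the SAP does not give them.** Inter-eye correlation of growth ρ = 0.5 to 0.9; SD of the right-left length difference D = 0.10 to 0.50 mm; linear growth; reading-error SD 0.01 mm; complete data. I take the model to include treatment by visit, as Table 3 requires.

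**Formulas.** Code the visits as t = 0, 1/3, 2/3, 1, so Σ(t − t̄)² = 5/9 and Σt² = 14/9.

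- True variance of the 18-month contrast, n per arm: 2 × 0.0324 × (1 + ρ)/2 / n.
- Model variance: 2s²/n, where s² is the expected within-child sum of squares divided by 7: s² = [(5/9)(0.0324)(1 + ρ) + 2D² + (14/9)(0.0324)(1 − ρ) + 7 × 0.01²] / 7.
- Ratio R = model SE / true SE (n cancels). One-sided error at a true difference of 0.13 mm = Φ(−1.96R). Power at a true difference of 0 = Φ(0.13/true SE − 1.96R).

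**Worked case, ρ = 0.9, D = 0.10.** s² = (0.0342 + 0.0200 + 0.0050 + 0.0007)/7 = 0.00856. The true counterpart is 0.0324 × 0.95 = 0.03078. R = √(0.00856/0.03078) = 0.53; error = Φ(−1.03) = 15%.

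| D (mm) | R, for ρ = 0.9 to 0.5 | One-sided error at the margin |
|---|---|---|
| 0.10 | 0.53-0.65 | 10-15% |
| 0.20 | 0.75-0.88 | 4-7% |
| 0.25 | 0.88-1.02 | 2.2-4.3% |
| 0.30 | 1.01-1.17 | 1.1-2.4% |
| 0.40 | 1.29-1.48 | 0.2-0.6% |
| 0.50 | 1.58-1.80 | ≤0.1% |

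R equals 1 at D = 0.24 mm (ρ = 0.5) and at 0.30 mm (ρ = 0.9). At D = 0.50, power is about 50% with 36 per arm (87-94% with a correct SE) and about 66% with 45 per arm (93-98%). Simulation of 8,000 trials per cell agreed with the ratios to within about 0.02-0.03. In the same trials, a child-level SE (two-eye mean change with a t reference) gave 2.0-2.8% error in every cell.

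**Range of D.** Section 5.1 caps anisometropia at "1.50 D cycloplegic spherical equivalent refractive error". At the SAP's 0.13-0.15 mm per 0.25 D that is 6 × 0.13 = 0.78 to 6 × 0.15 = 0.90 mm. It is a maximum and does not fix the SD. A uniform spread up to it would have SD 0.78/√3 = 0.45 to 0.90/√3 = 0.52, so 0.50 is about the upper end.

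**Adding only an eye intercept.** This removes D but not growth. s² becomes [(10/9)(0.0324) + 6 × 0.01²]/6 = 0.0061, so R = √(0.0061/0.03078) = 0.45 at ρ = 0.9 and √(0.0061/0.0243) = 0.50 at ρ = 0.5. Error is 16-19%, whatever D is.

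**Adjusted model.** The SAP does not say whether baseline axial length enters per eye or per child. In REML fits, per eye gave R = 0.41-0.59 and error 12-22%. Per child stayed near the unadjusted result (0.53-0.69 at D = 0.10; 1.53-1.73 at D = 0.50).

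**Joint ITT and PP rule.** With 45 per arm and PP assumed a random 67-80% of ITT, error at D = 0.10 is 6-11% (1.1-1.6% with correct SEs). Power at D = 0.50 is 37-49% (80-94% with correct SEs).

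**Missing data.** With 20% missing completely at random, clustered SEs gave 2.0-3.1% error. In one assumed MAR pattern, half of the 40% fastest-growing DIMS children at 12 months miss month 18, while OKL dropout is random. The random-intercept estimate then moves by −0.025 to −0.029 mm (19-22% of the margin) in favour of DIMS, and clustered SEs still give 12-13% error. An unstructured child-level covariance kept bias within 0.001 mm.

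**The case against.** **Direction and size are not known.** At D = 0.25-0.30 mm the error is close to nominal, and above that the test is conservative. This stands: the SAP cannot show which way the interval errs. But a rule that meets its 2.5% only if an unstated quantity falls in a narrow band is not controlled.

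**The 0.50 mm end is weakly based.** It applies a within-eye relation over time to a difference between eyes and assumes a uniform spread. This also stands, and that row is illustrative.

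**The joint rule lowers the error.** It does, to 6-11% at D = 0.10, still well above 2.5%. It also lowers power further at the other end.

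**The MAR example is a chosen pattern.** With the same rule in both arms the shift was about −0.002 mm, and with only half of the DIMS dropout tied to growth about −0.007 mm. The 20% is dropout assessed one month after the last inclusion, not missing month-18 readings, and 4.2 offers dropouts an 18-month examination for a sensitivity analysis. The example shows what can happen and does not predict it.

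**Robust SEs and bootstrapping are already available.** The wording is open-ended, and the participant is the natural cluster. Participant clustering would repair the width. However, its use depends on plots that do not target correlation within eye or over time, and the cluster or resampling unit is not named.

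**Conclusion.** Wrong as written. The primary interval's standard error is not the sampling error of the 18-month difference, so the stated one-sided 2.5% is not assured. Under the assumptions above, the error runs from 10-15% (right-left SD 0.10 mm) to at most 0.1% (0.50 mm), with substantial loss of power at the upper end. The figures rest on linear growth, complete data and the assumed inter-eye inputs. The lack of control over the width does not depend on any one of those values. This must be settled before the analysis.

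A lesser point, of efficiency only, lies outside this verdict. Baseline covariates entered as main effects cancel from change since baseline (exactly so in complete data without the non-wear term), so they do not bring the promised gain in precision. With an assumed R² of 25%, four covariates and 72 children, real adjustment would reduce the SE by about 11%: √(0.75 × 69/65) = 0.89.

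**What to change.** In 6.2 and the Table 3 and 5 footnotes, pre-specify one of the following for both ITT and PP, as the default and not as a fallback:

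- participant-clustered robust standard errors with a t reference; or
- a covariance with unstructured visits or a random slope at child level, plus eye nested in child.

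An eye intercept alone is not enough. Clustering corrects only the width. Because 6.4 relies on the model under MAR, the covariance option, or both together, fits the SAP's own assumption better. State also whether baseline axial length enters per eye or per child.

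Cost: SAP wording and minor Stata code, no new data. The interval may widen or narrow.

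Optional, for the efficiency point: in the adjusted analysis, model the 6-, 12- and 18-month lengths (or changes) on baseline length, age, refraction and myopic parents with their visit interactions, and keep baseline out of the response. This rewrites the adjusted model and the adjusted baseline rows of Tables 3 and 5.

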4.2	Adherence/compliance and protocol deviations Define adherence/compliance and how this is assessed in the study. Define protocol deviations and which protocol deviations will be summarized and presented	Main challenges: - Treatment adherence : Degree of adherence is assessed by patient-reported days without OKL or hours without DIMS between visits as "No-wear". "No-wear" is included in the mixed effects model as a time-varying post-randomisation variable (see 6.2) and in a sensitivity analysis (see 6.3). Missing measurements is assumed to be best case = 0 days/hours without OKL/DIMS. Day time hours is assumed to be 16 hours. Following defines the binary definitions of adherence: -- Low adherence (in the 6-month period between visits) 
 OKL: > or = 75% of days without OKL DIMS: > or = 75% of hours without DIMS -- Moderate Adherence (in a 6-month period) 
 OKL: 25-75% of days without OKL DIMS: 25-75% of daytime hours without DIMS -- High Adherence (in a 6-month period) 
 OKL: < or = 25% of days without OKL DIMS: < or = 25% of daytime hours without DIMS OKL: Each eye contributes with 50% of adherence; E.g. The right eye has 25% of days without OKL and the left eye has 75% of days without OKL, which gives a total % days without OKL of: $(0.25/2) + (0.75/2) = 50\%$, corresponding to moderate adherence. - Technical error in the reading of the autorefractor apparatus output at baseline resulting in four children included without correct cycloplegic refraction, assuming random error. The true output was available for analysis. No children were excluded by this error. This is handled by making a sensitivity analysis (see 6.3) - Drop out at treatment allocation/follow-up , will be handled by offering the participant a follow-up examination corresponding to the 18-month visit (noting use of types of treatments used and days using treatment) and used in a sensitivity analysis (see 6.3).

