		
 - Ocular magnification correction algorithm of the choroid thickness for the key secondary outcome: -- Missing corneal radius is handled as 0 (= no correction for corneal radius). It is noted in which participants and visits this occur, to report how many measurements this will concern. -- Missing refractive error is handled as 0 (= no correction for refractive error). It is noted in which participants and visits this occur, to report how many measurements this will concern. -- Algorithm non-functioning in participants with a refractive error = 0 (e.g. the OKL group) and an axial length exceeding maximum to be handled in the algorithm. It is handled by calculating the theoretical refractive error for the relevant visit using the AL increase since baseline: -0.25D is added to the baseline cycloplegic refractive error for every 0.15 mm longer AL for males and every 0.13 mm longer AL for females (Jakobsen, Gehr & Moller 2020). It is noted in which participants and visits this occur, to report how many measurements this will concern.
4.3	Analysis populations Define analysis population i.e. intention-to-treat, per-protocol, complete case, safety population	
As adherence challenges are expected (see 4.2) both Intention to treat and a per-protocol approach will be performed.
 
The primary analysis will follow the intention-to-treat (ITT) principle, including all randomized participants regardless of adherence or protocol deviations.
 
A per-protocol (PP) analysis will be conducted as a sensitivity analysis, including participants with high or moderate adherence and no major protocol violations described in (4.2)
 
Missing data will be handled using mixed effects models under the missing at random (MAR) assumption (6.4). Additional sensitivity analyses will be performed to assess the impact of deviations

Section 5: Study population

5.1	Screening (if applicable) Describe screening data to determine eligibility (i.e. scoring and scales)	
Potential participants were preliminary referred from private ophthalmic practices to the Department of Ophthalmology, University Hospital of Southern Denmark, Lillebaelt Hospital, Vejle, Denmark, based on cycloplegic refractive error in relation to age. After screening, potential eligible participants and their guardians were invited to an information meeting.

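### Section 6.2 does not say whether the unadjusted or the non-wear-adjusted model decides non-inferiority, and the latter would not estimate the ITT effect

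*SAP*

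**What the plan says.** Section 6.2 specifies a linear mixed model of axial length on visit with a participant random intercept, and then: "The regression models will be reported as unadjusted, and as adjusted for the following covariates for a more precise result". The covariates are age, refractive error, axial length and number of myopic parents, all at baseline. The next sentence extends the same adjusted model: "The adjusted model will also be adjusted for time-varying post-randomisation variable to explain the performance bias". The variable added is described as "Non-wear (patient-reported as the participants total amount of days without OKL or hours without DIMS".

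The decision rule in 6.2 is that the upper 95% bound for DIMS minus OKL at 18 months "is equal to or below 0.13 mm, in both ITT and PP analyses". Section 4.1 gives the same margin without naming a model. Section 4.3 makes ITT primary, "including all randomized participants regardless of adherence or protocol deviations". Table 3 has an unadjusted and an adjusted block. The Figure 3 caption sets ITT and PP against the margin, each with and without adjustment. Section 6.3 moves on to superiority if non-inferiority is shown, again without naming a model.

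On wear, section 4.2 says that the variable "is included in the mixed effects model as a time-varying post-randomisation variable (see 6.2) and in a sensitivity analysis (see 6.3". For the adherence bands it uses percentages and states: "Day time hours is assumed to be 16 hours". Section 5.4 describes non-wear as binary and refers the reader to 4.2, 6.2 and 6.3.

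**The concern.** The trial has one confirmatory claim, and the rule for it fixes the populations but not the model. Because ITT and PP must both pass, the open choice is between two pairs of intervals, unadjusted and adjusted. If the pairs disagree, the SAP does not say which one carries the claim.

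The two candidates also answer different questions. The SAP itself calls non-wear post-randomisation. How much a child wears the device can depend on which device was allocated, and wear is part of how the device works. Holding it fixed removes whatever part of the DIMS-OKL difference runs through wear. The result is no longer the effect of assignment regardless of adherence, and the bias can go either way.

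A smaller point follows: the coding of non-wear in the model is unsettled (days for one arm and hours for the other, percentage bands, or binary). The key secondary outcome follows the same approach, but 4.1 calls secondary results exploratory, so little hangs on it there.

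**Working it through.** **1. Does any section name the deciding model?**

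| Place | Fixes | Leaves open |
|---|---|---|
| 4.1 | margin, 95% bound | model |
| 4.3 | ITT primary, PP as sensitivity | model |
| 6.2 | both ITT and PP must pass | model |
| Table 3 | reports both models | which decides |
| Figure 3 | plots both against the margin | which decides |
| 6.3 | superiority if upper bound is below zero | model |

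None does.

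**2. The plan's own sample size.** Inputs from 3.3: margin 0.13 mm, SD 0.18 mm, one-sided 0.025, power 80%, and a true difference taken as 0. Then n = 2 × (1.96 + 0.8416)² × 0.18² / 0.13² = 30.1, so 31 per group. The noncentral t gives power 0.799 at 31 and 0.812 at 32, which reproduces the stated 32.

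At 32 per arm the SE of a simple comparison is 0.18 × √(2/32) = 0.045 mm. Non-inferiority therefore needs an estimate of at most 0.13 - 1.96 × 0.045 = 0.042 mm. Shifts of a few hundredths of a millimetre matter.

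**3. Shift caused by conditioning on non-wear.** The SAP gives neither wear rates nor a wear effect. Assumed here: 0.10 mm extra growth per six months of full non-wear; steady non-wear f within a child; f entered per interval and 0 at baseline; one coefficient for both arms.

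At 0, 6, 12 and 18 months the extra growth is 0.10 × f × (0, 1, 2, 3), and the covariate is f × (0, 1, 1, 1). Baseline length varies far more than growth, so within-child contrasts set the coefficient. Centring both patterns:

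- cross-product: (-0.75)(-1.5) + 0.25 × (-0.5 + 0.5 + 1.5) = 1.5
- sum of squares of the covariate pattern: 0.5625 + 3 × 0.0625 = 0.75
- coefficient: 0.10 × 1.5 / 0.75 = 0.20 mm per unit of f

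Shift at 18 months on a proportion scale = -0.20 × (f_DIMS - f_OKL).

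**4. Effect on the decision.** For a mean estimate m, the approximate share concluding non-inferiority is Φ((0.0418 - m)/0.045), with the SE kept at 0.045. The last column is from simulation: ITT only, 32 per arm, SD 0.18 mm, cluster-robust SE. Its share without non-wear is about 3%. The true difference is 0.13 mm.

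| Non-wear DIMS / OKL | Shift (mm) | m (mm) | Formula | Simulation |
|---|---|---|---|---|
| model without non-wear | 0 | 0.13 | Φ(-1.96) = 2.5% | about 3% |
| 30% / 10%, proportion | -0.04 | 0.09 | Φ(-1.07) = 14% | about 16% |
| 20% / 15%, proportion | -0.01 | 0.12 | Φ(-1.74) = 4% | 4-5% |
| 10% / 30%, proportion | +0.04 | 0.17 | Φ(-2.85) = 0.2% | under 1% |

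In the last row, power at a true difference of 0 falls by the same formula from Φ(0.93) = 82% to Φ(0.04) = 52%.

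A separate simulation of the 18-month change alone assumed non-wear of 25% against 10% and 0.2-0.4 mm extra growth per full non-wear over 18 months. False non-inferiority rose from about 2.5% to 9-23%. With the wear rates reversed, power fell from about 81% to 51-29%.

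The shifts are smaller under milder assumptions. A loss of 0.05 mm roughly halves each. Non-wear independent between intervals cuts the 30/10 shift to about -0.01 mm.

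**5. Coding of non-wear.** On the 16-hour day of 4.2, six months of full non-wear is 182 days for OKL and 182 × 16 = 2,912 hours for DIMS. Suppose raw units share one coefficient, with 20% non-wear and equal spread in both arms. The coefficient is then 0.20/2,912 × (1 + 1/16)/(1 + 1/256) per unit, and the shift is -0.20 × 0.20 × 1.058 × (1 - 1/16) = -0.04 mm at equal relative wear. In simulation the share rises from about 3% to 14%. On a proportion scale, or with a split at 25%, equal wear gives no shift. With the split, 30/10 gives about -0.03 mm.

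**The case against.** The best case for the plan is that its text already leans one way. Section 4.3 defines the primary analysis regardless of adherence. The Table 3 footnote describes the model with no covariates. Adjustment enters 6.2 as an addition for precision, with non-wear there to explain performance bias. On that reading the unadjusted model decides and the non-wear model is a legitimate supportive analysis. In addition, "Study groups labelled as A & B is presented to the authors", which limits outcome-driven choice.

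This is fair, but it remains inference. No sentence says it, Figure 2 is titled as model-adjusted means, and Figure 3 puts both models against the margin. Group labels hide the arms but do not name a model.

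Three stronger readings are tempting and not supported:

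- *The primary analysis is biased as planned.* This would hold only if the adjusted model decided, and the SAP never says that it does or calls its estimate the ITT effect.
- *Raw days and hours will be entered together.* The wording in 6.2 may describe only how wear is reported. Section 4.2 offers percentages and 5.4 a binary form, so the coding is unsettled rather than wrong.
- *Larger error rates are due to non-wear.* Using the random-intercept model's own SE (about 0.027 mm in simulation with child-specific growth rates), the threshold becomes 0.13 - 1.96 × 0.027 = 0.077 mm. Starting rates of 9-12% and larger rises follow. The understated SE inflates both the start and the rise. That is a separate defect, and 6.2 does provide for robust SEs or bootstrapping if assumptions fail.

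**Conclusion.** The gap is real and concerns the trial's only confirmatory claim, so it must be closed before results are seen. The finding that no deciding model is named, and that one candidate conflicts with the ITT definition in 4.3, rests on the text alone and needs no assumption about wear.

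The size is illustrative. It depends on assumed wear rates, an assumed wear effect and steady non-wear within child. The rule in 4.2 that sets missing non-wear to zero was not modelled. Under the main assumptions the shift on a proportion scale runs from -0.04 to +0.04 mm, against a largest passing estimate of about 0.042 mm. False non-inferiority goes from about 3% to anywhere between under 1% and 16%, and is close to unchanged (4-5%) when wear is 20% and 15%. The figures show direction and order of size, not this trial's actual error rate. The coding of non-wear is a secondary point that needs clarification.

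**What to change.** 1. In 6.2, name the deciding model. For example: *Non-inferiority, and the superiority step in 6.3, are decided by the 18-month group-by-visit contrast (DIMS minus OKL) from the unadjusted mixed model, fitted identically in ITT and PP; all other models are supportive.* A model adjusted for baseline covariates only is an equally good choice. In that case baseline axial length should not be both a covariate and an outcome row. Mark the deciding intervals in Figure 3.
2. Move the non-wear-adjusted model to 6.3 as exploratory, outside the decision rule. Enter non-wear on one scale in both arms, as the proportion of scheduled wear time missed per interval: days missed / days for OKL, and hours missed / (16 × days) for DIMS.
3. Align the references to 6.2 in 4.2 and 5.4, and state one coding.

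The cost is SAP wording only. No new data are needed and the non-wear analysis is kept. Because the SAP was approved on 24 November 2025, with analysis planned for December 2025 in an open-label trial, the amendment should state its date relative to data access.
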